SAE	Serious Adverse Event	
SDV	Source Data Verification	
SOP	Standard Operating Procedure	
TMF	Trial Master File	

STUDY OVERVIEW		
Full title	Management of Patients with Chronic Liver Disease (CLD) admitted	
	to Hospital as an Emergency.	
Objectives	 To evaluate the impact of different patterns of service organisation, provision and delivery in the English NHS on patient care and outcomes. To identify processes of care that may be used to address the 	
	existing marked inequalities in health, improve patient experience, engagement with healthcare and survival.	
Type of trial	Mixed methods project: this application and protocol relates to quantitative data linkage work package.	
Trial design and methods	This quantitative component will use linked national datasets in combination with a detailed characterisation of general and specialist liver and critical care service provision and practice to study determinants of received care and clinical outcomes of CLD patients after a first emergency admission (EA), in the study period between 1 April 2009 and 31 March 2022 in the English NHS.	
Health condition(s) or problem(s) studied	Emergency hospital admissions of people with CLD.	
Target sample size	Data on approximately 100K subjects	
Trial duration per	Not applicable.	
participant:		
Main inclusion/exclusion criteria:	All adult patients with CLD with a first emergency hospital admission in the study period from 1 April 2009 to 31 March 2022 according to HES-APC data and classified according to ICD-10 diagnostic codes. Data from people who have chosen the National Data Opt-Out will be excluded from the study cohort.	
Statistical methodology	Multiple methods to be utilised: please see statistics plan in section	
and analysis:	9.	
STUDY TIMELINES	2 vears	
Study Duration/length	2 years	
Expected Start Date	01/09/2022	
End of Study definition and anticipated date	Completion of planned analyses and submission of final report. 01/09/2024	
Key Study milestones	Funding already awarded. REC approval 1/09/2022	
STORAGE of SAMPLES (if applicable)		
Human tissue samples	Not applicable	
Data collected / Storage	Only existing data will be used in this part of the study. All data	
	analysed will be de-identified at source. All storage and analysis of the	
	de-identified dataset will be at the London School of Hygiene and Tropical Medicine (LSHTM).	

NHS Foundation Trust

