Other relevant hospital trust-level characteristics to be included from NHS England datasets will be the relevant hospital size in beds, bed occupancy and transplant centre status.

Time period considerations

Up-to-date organisational characteristics of bed numbers, occupancy and transplant status will be available throughout the study period but characteristics from some data sources will need to be updated through direct contact with NHS hospital trusts.

Work Package 2: Understanding Determinants of Variation in Practice and Outcomes after Emergency Hospital Admission.

The study will use linked existing electronic patient-level healthcare data to map the full "patient journey" of patients with CLD. The patient journey will start from the first emergency hospital admission and we will examine determinants of Intensive Care Unit (ICU) admission, length of stay, inter-hospital transfer for specialist care or liver transplantation and in-hospital and longer term mortality.

We will use three existing national datasets linked at patient-level:

- Hospital Episodes Statistics (HES) data (inpatient, outpatient data, A&E attendances and ONS mortality data)
- Intensive Care National Audit and Research Centre Case Mix Programme (ICNARC-CMP) database
- UK Transplant Registry maintained by NHS Blood and Transplant

The research team analysing the data will not have access to patient identifiers. Please see the Data Flow Diagram attached as appendix 2.

We will include all adult patients with CLD disease who were admitted with a first emergency hospital admission in the study period from 1 April 2009 to 31 March 2022 according to HES-APC data, with an expected cohort size of about 100,000 CLD patients. Patients will be considered to have CLD according to ICD-10 diagnostic codes.

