Explicit coding schemes will be developed. We will create coding schemes that describe the clinical characteristics of the patients, including the nature and severity of the CLD, their comorbidities, and their adversity-related health issues. Coding schemes will also be developed to capture critical care admissions, predominantly based on data items available through linkage with ICNARC data but enhanced by also including information available in HES records of hospital admission and adult critical care episodes. In addition, we will derive measures that capture specific patterns of secondary care use in the year immediately after the first emergency admission, in terms of the number of planned outpatient visits, A&E attendances, planned and emergency readmissions, and the total time spent in hospital.

We now outline how we will address each of the specific objectives listed in section 3.1.

1. Time trends in acute secondary care for patients with chronic liver disease and its outcomes:

We will use the linked datasets to describe for each year in the study period the number of CLD patients who had an emergency admission, the proportion of these patients who had an admission to critical care and its duration, total length of hospital stay, readmission rate and total time spent in hospital within the first year, the rate of liver transplantation, and in-hospital and 1-year mortality.

2. Regional variation in acute secondary care for patients with chronic liver disease and its outcomes: We will estimate in the last 5 years of data the rate of emergency admissions for CLD per 100 000 people per year in 44 regions of England. We will estimate regional emergency admission rates without and with adjustment for patient and regional characteristics. In addition, we will analyse regional differences in outcomes.

3. Impact of regional clinical networks on referral patterns: The development of regional networks, shaped as hub-and-spoke models, will be explored by observing referral patterns after a first emergency admission of patients with CLD. We will identify the hub (a hospital that typically receives referrals) and the spokes (hospitals that typically refer patients) in each clinical network. The configuration and characteristics of these networks will be compared.

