7 ELIGIBILITY CRITERIA

7.1 Inclusion Criteria

The study will include all patients older than 18 years with chronic liver disease (CLD) who were admitted with a first emergency hospital admission between 1 April 2009 and 31 March 2022.

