7.2 Exclusion Criteria

A previous emergency hospital admission with chronic liver disease in the two preceding years.

People who have chosen to adopt the National Data Opt-Out.

8 **RECRUITMENT**

Not applicable: study working with existing routine data only.

A data flow diagram is appended as Appendix 2.

Hospital Episode Statistics (HES) data will be requested from NHS Digital for patients with a Chronic Liver Disease (CLD) diagnosis anywhere in their episodes in the study period (1 April 2009 to 31 March 2021). CLD diagnosis will be defined as ICD-10 codes in the range between B15-B19 or between K70-K77.

Analysts at NHS Digital will identify the patient cohort. They will send the identifiers of these patients (without any clinical data) to the Intensive Care National Audit and Research Centre (ICNARC) for linkage to ICNARC data.

Patients undergoing a liver transplant in England between one year before the study period to one year after the study period will be identified in The UK Transplant Registry, by NHS Blood and Transplant. The identifiers of these patients will be sent (without clinical data) to NHS Digital for linkage to HES.

De-identified cohorts of patients will be sent from NHS Digital, ICNARC and NHS Blood and Transplant to LSHTM for analysis, containing no patient identifiers. Pseudonymised study IDs will be used by the research team at LSHTM to link the three datasets.

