9 STATISTICAL METHODS

Please see section 4 above. Further, an overview of the statistical plan is presented below.

King's College Hospital NHS

NHS Foundation Trust

We will include all patients older than 18 years with chronic liver disease (CLD) who were admitted with a first emergency admission (EA) in the study period from 1 April 2009 to 31 March 2022. Patients will be considered to have CLD if they have a Hospital Episode Statistics (HES) inpatient record with an ICD-10 codes in the range between B15- B19 or between K70-K77. An EA will be identified based on an administrative HES code related to the method of admission. We will consider an EA to be a first-time occurrence if there is no record of a similar admission, with a minimum of in two preceding years of data available (the "look-back" period).

We will create coding schemes that describe the clinical characteristics of the patients, including the nature and severity of the CLD, their comorbidities, and their adversity-related health issues. Coding schemes will also be developed to capture critical care admissions, predominantly based on data items available through linkage with Intensive Care National Audit and Research Centre (ICNARC) data but enhanced by also including information available in HES records of hospital admission and adult critical care episodes. In addition, we will derive measures that capture specific patterns of secondary care use in the year immediately after the first EA, in terms of the number of planned outpatient visits, and A&E attendances, the number of planned and emergency readmissions, and the total time spent in hospital.

Specific research questions:

1. Time trends in acute secondary care for patients with chronic liver disease and its outcomes:

We will use the linked datasets to describe for each year in the study period from 1 April 2009 to 31 March 2022, the number of CLD patients who had an EA, the proportion of these patients who had an admission to critical care and its duration, total length of hospital stay, readmission rate and total time spent in hospital within the first year, the rate of liver transplantation, and in-hospital and 1-year mortality. Changes in these results over time (including changes in the period 2020-2022 as a result of the Covid-19 pandemic) will be determined with Poisson, logistic or linear regression models, depending on the nature of the dependent variable.

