2. Regional variation in acute secondary care for patients with chronic liver disease and its outcomes:

First, we will estimate the rate of EAs for CLD per 100 000 people per year in 44 regions. The numerator will be the number of CLD patients with a first EA and the denominator populations will be derived by aggregating the updated 2011 Census results for patients of 18 years and older in each region. We will use multilevel Poisson regression models to produce empirical Bayes estimates for regional EA rates without and with adjustment for patient and regional characteristics. We will analyse regional differences in critical care use during the EA, total length of hospital stay, readmission rate and total time spent in hospital within the first year, the rate of liver transplantation, and in-hospital and 1-year mortality. Multilevel regression models will be used to quantify the regional variation and to produce empirical Bayes estimates for each region. We will assess the impact of the Covid-19 pandemic on regional variation in EA rates and outcomes.

3. Impact of regional clinical networks on referral patterns: The development of regional networks, shaped as hub-and-spoke models, will be explored by observing referral patterns after a first EA of patients with CLD. We will create "super-spells" for each patient and identify within this super-spell the hospital of the EA and the hospital trust where most of the care was provided. These results will be used to identify the hub (a hospital that typically receives referrals) and the spokes (hospitals that typically refer patients) in each clinical network. The configuration and characteristics of these networks (e.g., in terms of regional coverage, number and characteristics of referred patients, type of

care provided predominantly in the hub and spokes, changes to referrals pre- and post- Covid-19)) will be compared.

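### The regional emergency-admission rate leaves opted-out patients (and, read literally, 18-year-olds) out of the numerator but keeps them in the census denominator, so absolute rates are too low

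*Protocol*

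**What the plan says.** **Numerator.** Section 9, question 2: "The numerator will be the number of CLD patients with a first EA". These patients are drawn from the study cohort, which is restricted in two ways.

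- Opt-out: the Study Overview states "Data from people who have chosen the National Data Opt-Out will be excluded from the study cohort". Section 7.2 lists the same exclusion: "People who have chosen to adopt the National Data Opt-Out".
- Age: Section 7.1 reads "The study will include all patients older than 18 years with chronic liver disease (CLD", and Section 9 repeats the older-than-18 rule. The Study Overview and Section 4 say only adult; Section 4 has "We will include all adult patients with CLD disease who were admitted with a first emergency hospital admission".

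**Denominator.** The next words of question 2 fix it: "the denominator populations will be derived by aggregating the updated 2011 Census results for patients of 18 years and older in each region". Opted-out residents and 18-year-olds are both counted there.

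**Period and model.** Section 4, question 2 limits the regional rates: "We will estimate in the last 5 years of data the rate of emergency admissions for CLD per" 100,000 people a year, in 44 regions. Section 9 plans multilevel Poisson models with empirical Bayes estimates, without and with adjustment for patient and regional characteristics, and an assessment of Covid-19 effects on regional variation. No step in either section aligns the two populations.

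**The concern.** A rate is interpretable only if everyone in the denominator could have appeared in the numerator. Here an opted-out adult adds to the population at risk but can never be counted as a case. The two planned modelling steps do not address this. Empirical Bayes shrinkage reduces random noise, and covariate adjustment is aimed at case mix and regional context, not at unequal ascertainment.

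Regional variation in acute care use is the second listed objective, and the findings are meant to inform commissioning. The absolute EA rate is a headline output and would be understated. If opt-out uptake happened to vary between the 44 regions, part of the reported variation would reflect uptake rather than admissions. More data would not remove that part.

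**Working it through.** The protocol states no EA rate, census count or opt-out proportion, so there is no figure to reproduce. The check is rate algebra with assumed shares.

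**Definitions**
- C = all first-EA cases older than 18 in a region; N = census population aged 18 and older.
- o = share of C removed for opt-out (assumed).
- s = share of N aged exactly 18 (assumed 1.5%, range 1.2-2.0%).

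**Absolute rate**
- Rate as planned = C(1 − o)/N.
- Rate in people older than 18 = C/[N(1 − s)].
- Planned/true = (1 − o)(1 − s).

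| o | s | planned/true |
|---|---|---|
| 0 | 1.5% | 0.985 |
| 1% | 1.5% | 0.99 × 0.985 = 0.975 |
| 3% | 1.5% | 0.97 × 0.985 = 0.955 |
| 5% | 1.5% | 0.95 × 0.985 = 0.936 |
| 10% | 1.5% | 0.90 × 0.985 = 0.887 |

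With matched populations the factor is 1.00. Both mismatches lower the rate.

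**Ratio of two regions with equal true rates**, from opt-out alone = (1 − o_A)/(1 − o_B):
- equal uptake: 1.00
- 3% v 7%: 0.97/0.93 = 1.04
- 3% v 8%: 0.97/0.92 = 1.05
- 2% v 10%: 0.98/0.90 = 1.09

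From the age mismatch alone, with s = 1.2% v 2.0%: 0.988/0.980 = 1.008.

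**Scale against sampling error.** Section 2 gives about 9,000 first EAs a year. Over five years and 44 regions, taken as equal in size, that is 9,000 × 5/44 ≈ 1,023 events per region.
- SE of a log rate = 1/√1,023 = 0.031.
- SE of a log ratio of two regions = √(2/1,023) = 0.044.
- A ratio of 1.05 (0.97/0.92 = 1.054) is ln(1.054)/0.044 ≈ 1.2 standard errors; 1.09 is ln(1.089)/0.044 ≈ 1.9.
- Nationally, 45,000 events give an SE of 1/√45,000 = 0.005, so even a 1% opt-out share is about two standard errors of the overall rate.

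**The case against.** Several counter-arguments have force.

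- **Uniform uptake would leave regional ratios intact.** This stands. A reader might infer that the bias does vary between regions and over time, but no section gives opt-out uptake by region or year. That variation is an assumption. The time element is narrower still, because Section 4 restricts these rates to the last five years and question 1 (yearly trends) states no census denominator. Only the Covid-19 comparison of regional rates could be touched.
- **The age part is trivial.** Largely right. It is about 1-2% by assumption and nearly constant across regions, and older than 18 may simply be loose wording for adult. If 18-year-olds are in fact included, this part vanishes. It is an editorial inconsistency that should still be settled.
- **Regional variation is far larger.** Section 2 cites 8.5-fold variation in hospital admissions. That is between Clinical Commissioning Groups and not the 44 regions, so it gives perspective but does not make a bias of a few percent harmless in the absolute rates.
- **Section 9 is an overview, and corrections belong in a SAP.** The form of the offset can wait for a SAP. The denominator, however, is not left open: the protocol specifies it, and what it specifies does not match the cohort.

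A further reading is tempting: only survivors can opt out later, so early-year 1-year mortality would be inflated and a false improvement would appear. The documents do not say at what date opt-out status is applied or how the records of people who have since died are handled. With an assumed true mortality of 40%, removing 5-10% of survivors only would give 0.40/(0.40 + 0.60 × 0.95) = 41.2% to 0.40/(0.40 + 0.60 × 0.90) = 42.6%. Suppose instead that 75% survive the EA, 30% of those are alive at five years (Section 2 says nearly 70% die), and 5-10% opt out only then. The result is 40.5-40.9%. The size depends on timing that is not given.

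**Conclusion.** The mismatch between numerator and denominator is real, is written into the protocol and is uncorrected. Its certain consequence is that absolute regional EA rates are too low by the opt-out share among cases, plus about 1-2% if 18-year-olds are truly excluded. The opt-out share itself is unknown from the documents; the 1-10% range used here is an assumption.

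Distortion of regional ratios, or of the Covid-19 comparison, is conditional on uptake that differs by region or period. It would be about 1.05 to 1.09 under the assumed contrasts and nil under equal uptake. Survivor-only removal in the mortality trend is not a demonstrated bias and merits at most an optional sensitivity check. The point should be corrected because the remedy is simple, but it does not threaten the study's main conclusions on the evidence in the protocol.

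**What to change.** 1. Use one age boundary in the Study Overview, Section 4, Section 7.1 and Section 9 (cohort definition and question 2 denominator).
2. Section 8 has NHS Digital identify the cohort. Ask it for aggregate opt-out counts or shares by region and year, and scale the regional denominator or Poisson offset by one minus that share. State which share is used: the share among cases recovers the whole-population rate, while the share among adult residents gives the rate in people who have not opted out.
3. If these figures cannot be released, report the regional rates with bounds over a stated range of opt-out shares, and name the mismatch as a limitation.
4. Optionally, state the date at which opt-out status is applied and, if it falls after follow-up, check how sensitive the 1-year mortality trend is to it.

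The cost is a protocol wording change, one aggregate data request (possibly with small-number suppression) and a modified offset. No further patient-level data are needed.

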4. Impact of regional, hospital and patient characteristics on critical care use of chronic liver disease patients who had a first emergency admission: We will explore the association between which of the regional characteristics (e.g., network arrangements, prevalence of CLD, use of transplantation), hospital characteristics (e.g., transplant centre status, specialist staffing, ICU capacity, ICU case-mix), and patient characteristics (e.g., type of CLD and comorbidity, age, sex, socioeconomic deprivation) are associated with the proportion of cases admitted to critical care, their clinical condition at critical care admission, the duration of critical care, and the proportion of cases for whom critical care was withdrawn. We will also explore changes in critical care use as a result of the Covid-19 pandemic. Multilevel logistic regression models will be used to estimate adjusted odd ratios that capture the impact of the regional, hospital and patient characteristics and the Covid-19 pandemic on critical care use.

5. Critical care use and clinical outcomes after a first EA in patients with CLD: We will characterise hospitals according to the proportion of patients that are admitted to critical care and whether they were admitted to critical care early or late in order to explore to what extent hospitals with more frequent and earlier critical care admissions of CLD patients after an EA have better short-term outcomes (in-hospital mortality and readmissions, total time spent in hospital and mortality during the year following the EA). The results will be analysed using multilevel logistic regression including the level and timing of critical care use as hospital-level characteristics with adjustment for key patient characteristics, including age, sex, socioeconomic deprivation, and comorbidity.

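### The regional emergency admission rate in question 2 counts cases and population over different people, and its patient-level adjustment is tied to a denominator described only by region

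*Protocol*

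**What the plan says.** Section 9 of the protocol, question 2, sets the target: "we will estimate the rate of EAs for CLD per 100 000 people per year in 44 regions". It defines the top of the fraction, "The numerator will be the number of CLD patients with a first EA", and the bottom, "the denominator populations will be derived by aggregating the updated 2011 Census results for patients of 18 years and older in each region". Multilevel Poisson models are then to give "empirical Bayes estimates for regional EA rates without and with adjustment for patient and regional characteristics". Section 4 repeats the intention, "We will estimate regional emergency admission rates without and with adjustment for patient and regional characteristics", and limits the rate to the last five years of data.

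The case definition is in section 7. Section 7.1 reads "The study will include all patients older than 18 years with chronic liver disease (CLD", and section 9 uses the same age wording. Section 7.2 lists as an exclusion "People who have chosen to adopt the National Data Opt-Out", and the Study Overview table says the same.

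Question 2 does not name its patient characteristics. The nearest list is an example list under question 4, on critical care use: "patient characteristics (e.g., type of CLD and comorbidity, age, sex, socioeconomic deprivation".

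**The concern.** A population rate needs a numerator drawn from the people counted in its denominator. Here two stated rules break that link. A person who has opted out is removed from the cases but still counted in the census population. On a literal reading, an 18-year-old is in the population but cannot be a case. Both push the rate down. The opt-out rule matters more, because opt-out may vary between regions, and variation between regions is what question 2 sets out to measure.

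The second issue is the adjustment. A rate can be adjusted at patient level only for characteristics known for the population as well as for the cases. Age, sex and area deprivation can meet that condition if the denominator is split by them. CLD type, severity and comorbidity cannot, because a general population count does not carry them. Question 2 neither limits the adjustment to the first group nor says the denominator will be split.

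The regional estimates are meant to inform national and regional commissioning (section 20). A region could therefore look better or worse than it is because of who opted out, or because an adjustment had no effect.

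**Working it through.** The protocol states no regional rate, so there is no figure to reproduce.

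**1. Inputs.** From the protocol: about 9,000 first emergency admissions a year (section 2), 44 regions (sections 4 and 9), five years of data (section 4). Assumed: the opt-out shares and the adult population.

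**2. Scale.** 9,000/44 = about 205 first admissions per region per year, or about 1,023 over five years. For an assumed 35 to 50 million adults, the crude rate is 9,000/35,000,000 = 25.7 down to 9,000/50,000,000 = 18.0 per 100,000 per year.

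**3. Opt-out.** Let N be the true number of first admissions in a region, P its adult population, and q the opt-out share among those patients. The rate as written is N(1 − q)/P, so it is understated by the factor 1 − q. For two regions with equal true rates, the apparent ratio is (1 − q1)/(1 − q2):

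- Equal opt-out: ratio 1.00. The level is too low but the comparison is intact.
- 2% against 4% (assumed): 0.98/0.96 = 1.02.
- 2% against 10% (assumed): 0.98/0.90 = 1.09.

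For comparison with chance, the standard error of the log ratio of two average-sized regions over five years is about √(2/1,023) = 0.044 (Poisson variation only). The last case gives ln(1.089) = 0.085, about 1.9 standard errors. The 2% against 4% case gives ln(1.021) = 0.021, about half a standard error.

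**4. Age limit.** If a is the share of a region's adults who are 18, and cases start at 19, the rate for those over 18 is understated by the factor 1 − a. The protocol gives no age distribution. Only one year of age is involved.

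**5. Adjustment with a characteristic known only for cases.** Split the cases by CLD type t (0 or 1), with the same regional population as offset for each type: log mean = α_r + βt + log P_r. The Poisson fit matches each region's total Y_r, so α_r = log(Y_r/P_r) − log(1 + e^β). Every region shifts by the same constant and the regional contrasts do not change. A simulation agreed: the largest difference between adjusted and unadjusted regional log rates was 7 × 10⁻¹⁴, which is rounding error.

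**6. Adjustment with a split denominator.** One data set was simulated with 44 regions, 5 × 9,000 = 45,000 admissions, an assumed 44 million adults, an assumed regional standard deviation of 0.2 on the log scale, and illustrative rate ratios for age, sex and deprivation. Regions were fitted as fixed effects.

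| Regional log rate | Correlation with true regional effect | Root mean squared error |
|---|---|---|
| Unadjusted | 0.762 | 0.141 |
| Adjusted, denominator split by age, sex and deprivation | 0.986 | 0.033 |

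The values depend on the assumed inputs. They show that the adjustment works once the population is split, whereas step 5 shows that it does nothing for a case-only characteristic.

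**The case against.** The strongest reply is that section 9 calls itself an overview. Covariate lists and denominator strata normally belong in a statistical analysis plan, which is not shown. The list with CLD type and comorbidity is only an example list, and it belongs to a question about patients already admitted. It also contains age, sex and deprivation. Aggregating to region does not rule out strata, and selecting adults already requires a source with age detail. This stands: the absence of a covariate list is not an error in itself. What remains is that the adjustment, as described, needs a limit to variables the population can supply.

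A reader might infer that the adjusted rate cannot be derived at all. The documents do not support that. Age, sex and area deprivation can be used if the source tabulates them, which is an assumption about the census product. Regional characteristics can enter as region-level covariates even with one total per region.

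The opt-out effect may also be small. The 2% to 10% range is assumed, and its ends make a worst-case pair. Scaling by the general opt-out share is right only if people with CLD opt out at that rate, and nothing in the protocol shows this. That is a reason for a sensitivity analysis rather than a correction of the main result. The age wording may be a slip: 'older than 18' could mean past the 18th birthday, and elsewhere the protocol simply says adult. No regional distortion from it is shown.

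The reply that detail belongs in an analysis plan does not reach the coverage mismatch. The exclusion and the denominator are both stated rules in this protocol, and they do not match.

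**Conclusion.** The concern holds for coverage and, more narrowly, for adjustment. As written, the regional rate takes its cases from people over 18 who have not opted out and divides by everyone aged 18 or more. The rate is understated by the opt-out share, plus a probably small amount from the age limit on its literal reading. Regional comparisons are distorted only so far as opt-out differs by region. The size is unknown: the ratio is 1.00 with equal opt-out and 1.09 with 2% against 10%, and both shares are assumptions.

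The planned patient-level adjustment has an effect only for characteristics tabulated in the denominator. For those known only for cases it leaves regional contrasts unchanged.

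A reader might also infer that adjusting for case mix would remove the disease burden being measured. The documents do not support this. A case-only covariate changes nothing, and the unadjusted rate is reported beside the adjusted one. Burden could be absorbed only if a regional measure such as CLD prevalence or a regional case-mix share were entered as a covariate, and question 2 does not say so.

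**What to change.** In section 9, question 2, or in the analysis plan:

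- Use the same age limit for cases and population, and align the wording in section 7.1.
- Tabulate denominators by region, year, age band, sex and area deprivation, and limit patient-level adjustment of the admission rate to those variables. Keep CLD type, severity and comorbidity for outcomes among admitted patients.
- Add a sensitivity analysis that multiplies each regional denominator by one minus the regional opt-out proportion. State its assumption: if the opt-out share among people with CLD equals the population share q, then N(1 − q)/[P(1 − q)] = N/P, and otherwise the correction is only partial.

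The cost is a finer tabulation of population counts already planned, regional opt-out proportions from an outside source, and one extra analysis. No change to the patient data request is needed.
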